early syphilis; in addition, ceftriaxone (500 mg intramuscularly once) is effective for treating *N. gonorrhoeae* infection, and doxycycline (100 mg orally twice daily for 7 days) effective for treating *C. trachomatis* infection.⁸ However, the current suggested dose of ceftriaxone for early syphilis (1 g intramuscularly or intravenously once daily for 10-14 days) is inconvenient as an outpatient treatment option. Ceftriaxone is long-acting, with treponemacidal levels remaining at 24 hours following injection. According to a small clinical trial, single-dose ceftriaxone achieved a serological response similar to that of BPG.⁹ Considering the high rate of sexually transmitted co-infections, combination therapy of single-dose ceftriaxone plus 7-day doxycycline for early syphilis may provide convenience and benefit to treatment of *N. gonorrhoeae* and *C. trachomatis* co-infections at a single clinic encounter. In the present study, we aim to compare the efficacy of ceftriaxone plus doxycycline versus BPG plus doxycycline as the treatment for early syphilis among PLWH.

Methods

1. Study design: randomized controlled, open-label, non-inferiority study

2. Study site: infectious diseases clinics at the National Taiwan University Hospital (NTUH)

3. Study duration: 2022-2025

4. Enrolled criteria:

(1) PLWH aged 20 years or more

(2) PLWH with early syphilis (i.e. primary, secondary, or early latent syphilis), confirmed by a positive rapid plasma reagin (RPR) titer with a reactive *Treponema pallidum* particle agglutination (TPPA) assay.

(3) PLWH has provided informed consent

*A participant with repeated syphilis can be repeated enrolled after signing an informed consent if the previous episode of early syphilis was successfully treated with achieving at least a 4-fold decrease in RPR titers and 48-week follow-up is completed.

5. Exclusion criteria:

(1) PLWH with RPR titers of less than 4

(2) Exposure to antibiotics with activity against *T. pallidum*, such as penicillins, third-generation cepheems, doxycycline, or macrolides, within the preceding 4 weeks

(3) A known or suspected infection other than syphilis requiring additional treatment with an antimicrobial active against *T. pallidum*

(4) A history of intolerance to penicillin, ceftriaxone, or doxycycline

(5) Pregnancy

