TP-PCR	v				v	v	v	v	v
Bacterial STIs	v				v				
RAM	v								

8. Duration of study: Participants will be followed for at least 48 weeks.

9. Primary outcome:

Serologic response at month 6 (defined as either a 4-fold or greater decline in RPR titer compared to baseline or being RPR-nonreactive)

10. Secondary outcomes:

(1) Microbiologic response of syphilis (defined as *T. pallidum* PCR Ct value >38) at week 4

(2) Microbiologic response of bacterial STIs (defined as negative PCR results) at week 4

(3) Serologic response at months 3 and 12

(4) Safety of study treatment recorded by using a diary (all adverse events will be coded and graded according to Common Terminology Criteria for Adverse Events [CTCAE] v4.0.)

(5) Adherence evaluation (the noting of tablet intake in the diary for the 7 days of the treatment period)

11. Futility stopping rules:

(1) In the proof-of-concept phase, microbiologic and/or serologic response of syphilis

(microbiologic response was defined as *T. pallidum* PCR Ct value >38, and serologic response was defined as at least a 4-fold decrease in RPR titers) at week 4 will be compared between study groups. The non-inferiority margin of 10% will be used as the futility stopping rule in the proof-of-concept phase.

(2) Participants with treatment failure at week 24 will receive standard-of-care treatment (BPG 2.4 MU intramuscularly once). Treatment failure is defined as at least a 4-fold increase in RPR titers compared with the baseline RPR or at least a 4-fold increase in RPR titers after achieving serologic response during follow-up. Participants who received additional treatment with an antimicrobial active against *T. pallidum* (i.e. penicillins, third-generation cepheems, doxycycline, or macrolides) will also be excluded from the study.

(3) The continuation phase will be conducted only if microbiologic response of syphilis is non-inferior in the ceftriaxone plus doxycycline group compared with the BPG plus doxycycline group.

Laboratory investigations

1. *T. pallidum* PCR:

T. pallidum PCR will be performed on specimens from oral rinse, urine, rectal sites, blood, and lesions of syphilis. Treponemal DNA will be extracted with the QIAamp DNA mini Kit. The diagnostic PCR assay will be used to amplify the 47 kDa protein membrane gene (*tpp47*).

2. Bacterial STIs screening:

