The screening for bacterial STIs, including *C. trachomatis*, *N. gonorrhoeae*, *Trichomonas vaginalis*, *Mycoplasma* spp., and *Ureaplasma* spp.) will be performed on self-collected specimens from oral rinse, urethral, and rectal sites with the use of multiplex real-time PCR assay on an automated system.

3. Resistance-associated mutation of *T. pallidum*

Single-nucleotide polymorphisms (SNPs) will be determined at positions A2058G or A2059G of the 23S rRNA gene, as well as positions 965–967, 926–928, 939 and 1058 of the 16S rRNA gene.

Statistical analysis

According to the previous randomized controlled, open-label study conducted by Cao Y et al, the serological response of early syphilis at 6 months of follow up was observed in 90.2% in ceftriaxone group and 78.0% in BPG group.¹⁰ Therefore, at least 150 participants would be

required for each treatment group to detect a between-group difference, with a two-sided significance level of 5% and a power of 80%. The intention-to-treat population is defined as all patients who undergo randomization except for those who do not provide consent for the use of their data. The analyses will be performed through the FDA snapshot algorithm in the ITT population, which categorizes outcomes into success, failure, and no data in window. The Categorical variables will be compared by Fisher's exact test or Chi-square test. Non-categorical variables will be compared by Mann-Whitney U test. Factors with P value ≤ 0.2 , or with biological significance will be included for multivariate analysis. Logistic regression analysis will be used to determine the factors associated with serologic responses after treatment. All comparisons will be two-tailed and a P value <0.05 is considered significant. All statistical analyses were performed with the use of STATA software version 17.0 (Stata Corporation, College Station, TX).

References

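### The 150 per group is sized to detect a 12.2-point difference and uses no margin, so power for the declared month-6 non-inferiority objective is not established

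*Combined protocol and SAP*

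**What the plan says.** Methods item 1 reads "Study design: randomized controlled, open-label, non-inferiority study". The primary outcome (Methods item 9) is binary: serologic response at month 6, based on the RPR titer.

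The Statistical analysis section starts from a cited randomised open-label trial in which response at 6 months was "90.2% in ceftriaxone group and 78.0% in BPG group". From this it derives a minimum of 150 per group, a number described as "required for each treatment group to detect a between-group difference, with a two-sided significance level of 5% and a power of 80" per cent. Enrolment matches: Methods item 7 plans 50 per group in the proof-of-concept phase and 100 per group in the continuation phase.

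The one numerical margin is in Methods item 11(1): "The non-inferiority margin of 10% will be used as the futility stopping rule in the proof-of-concept phase". That rule concerns microbiologic and/or serologic response at week 4. No margin is given for the month-6 primary outcome. The Statistical analysis section lists Fisher's exact, chi-square and Mann-Whitney tests, all two-tailed at 0.05, and gives no confidence-interval criterion for non-inferiority.

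On expected efficacy, the Background reports from a small trial that "single-dose ceftriaxone achieved a serological response similar to that of BPG", and says an alternative as effective as BPG is needed.

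**The concern.** The hypothesis declared and the hypothesis powered are different. A non-inferiority trial asks whether the new regimen is worse by more than a stated margin. The sample size answers another question: whether a difference of 90.2 − 78.0 = 12.2 points, in favour of the new regimen, would be detected. A reader who sees a non-inferiority design and 80% power will take the 80% to refer to non-inferiority, which it does not.

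This matters most if the two regimens are about equally effective, the usual planning case for non-inferiority. Power then depends on the margin and the common response rate. The plan fixes neither for month 6, and over the range of its own two rates power moves a long way. If non-inferiority were not shown, nobody could tell from the plan how likely that result was for an equally effective regimen.

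**Working it through.** **Inputs from the documents.** Response 90.2% (ceftriaxone) and 78.0% (BPG); two-sided alpha 5%; power 80%; 150 per group (Statistical analysis). Allocation 1:1 (Methods item 6). Margin 10 points, stated for week 4 only (Methods item 11(1)).

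**Assumptions made here, not in the plan.** The 10-point margin is carried over to month 6; one-sided alpha is 2.5%, equivalent to the lower limit of a two-sided 95% interval; there are no dropouts. The equal-rate scenarios are also mine.

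**Step 1: the plan's own figure, as a superiority calculation.** With mean rate p̄ = (0.902 + 0.780)/2 = 0.841 and d = 0.122:

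n = [1.96·√(2·0.841·0.159) + 0.8416·√(0.902·0.098 + 0.780·0.220)]² / 0.122²
= [1.0136 + 0.4291]² / 0.014884 ≈ 139.9, so 140 per group.

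The continuity-corrected version gives 156. The stated 150 lies between the two. Power at 150 is 82.7% by the chi-square approximation and 79.2% by exact Fisher test. So 150 is a superiority-type number, and broadly adequate for that purpose.

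**Step 2: non-inferiority power at 150 per group.**

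Power = Φ[(0.10 − (p_BPG − p_CRO))/SE − 1.96], with SE = √{[p_BPG(1 − p_BPG) + p_CRO(1 − p_CRO)]/150}.

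With equal true rates p, the number per group for 80% power is (1.96 + 0.8416)²·2p(1 − p)/0.10².

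| True response, BPG / ceftriaxone | SE | Power at 150 | n per group for 80% |
|---|---|---|---|
| 78.0% / 78.0% | 0.0478 | 55.2% | 270 |
| 84.1% / 84.1% (midpoint) | 0.0422 | 65.8% | 210 |
| 90.2% / 90.2% | 0.0343 | 83.0% | 139 |
| 78.0% / 90.2% (the plan's rates) | 0.0416 | above 99.9% | 42 |

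For the last row: (0.10 + 0.122)/0.0416 − 1.96 ≈ 3.37, so power is 0.9996. Exact calculations with the Newcombe interval give 55.7%, 65.4% and 80.9% for the three equal-rate rows, so the normal approximation is slightly generous at the highest rate.

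**Step 3: where 80% is reached.** With equal arms, SE must be at most 0.10/2.8016 = 0.0357. Then p(1 − p) ≤ 150·0.0357²/2 ≈ 0.0956, so p is about 89.3% or more. With BPG at 78%, a true ceftriaxone advantage of 3 points gives 79.7%.

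**Step 4: sensitivity to the margin.** At equal 78% response, power at 150 is 39% for a margin of 8 points, 55% for 10, 74% for 12.5 and 88% for 15. Only the 10 is in the plan. Without a stated month-6 margin the power is undefined.

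**The case against.** The strongest reply is that 150 may be enough. Under the plan's own rates and a 10-point margin, non-inferiority power is above 99.9%, and assuming some advantage for the new arm is not in itself incompatible with a non-inferiority design. A common response near 90% would also do. This stands. A reader might infer that 150 per group has been shown to fall short of 80% for non-inferiority, but the documents do not support that: they set no month-6 margin, and under a borrowed one the answer runs from 55% to above 99.9%.

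Two other strong readings also go too far. One is that the sample size is miscalculated. It is not: 150 exceeds the uncorrected requirement of 140 for the comparison described. The other is that the Background commits the sponsor to equal efficacy. It reports one small trial's result and a need for an equally effective alternative; neither is a planning assumption.

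The true rate is also uncertain in both directions. Both arms add 7 days of doxycycline, which the Background names among the alternative treatments for early syphilis, so response could exceed 78%. Against that, the snapshot algorithm has a no-data category and no dropout allowance is stated. If missing data counted as non-success, an illustrative 70% in both arms would give about 47% power. The 55% is therefore one scenario, not a forecast.

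None of this makes 80% the non-inferiority power. That would require a margin, and none enters the calculation.

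**Conclusion.** The concern holds as a mismatch between design and hypothesis. The stated 80% is power to detect 90.2% versus 78.0%, and the plan does not establish power for its declared month-6 objective. That the 80% does not describe non-inferiority follows from the documents alone. The size of any shortfall does not: it rests on a 10-point margin borrowed from the week-4 rule, one-sided alpha 2.5% and an assumed pair of true rates. On those terms an equally effective regimen has about 55% power at the plan's BPG rate, 66% at the midpoint and 83% at the plan's ceftriaxone rate. The near-certain result needs a large true advantage for ceftriaxone, such as the plan's 12.2 points.

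**What to change.** Three wording changes, all in the Statistical analysis section:

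1. Label the 80% as power for a superiority comparison under 90.2% versus 78.0%.
2. State and justify a non-inferiority margin for serologic response at month 6. If the plan's 10 points are to be used, say openly that they are being extended from the week-4 rule and that one-sided alpha is 2.5%. State that the primary outcome will be judged by the two-sided 95% confidence interval for the difference in response against that margin, since the listed two-tailed difference tests do not address non-inferiority.
3. Give the resulting power with its assumptions. For a 10-point margin and 150 per group this is about 55%, 66% and 83% at equal true response of 78.0%, 84.1% and 90.2%, and above 99.9% under 90.2% versus 78.0%. A different margin needs new figures.

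This requires no extra participants, visits or tests. The cost is a protocol and SAP wording change, the work of justifying a margin, and a stated power that looks less favourable than 80% over much of the plausible range.

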6. Study procedures: participants will be randomized in a 1:1 ratio to receive ceftriaxone plus doxycycline or BPG plus doxycycline. Randomization will be stratified by the stage of syphilis and RPR titer at baseline.

Arm 1: single-dose ceftriaxone (1g intramuscularly once) plus doxycycline (100 mg orally twice daily for 7 days)

Arm 2: single-dose BPG (2.4 MU intramuscularly once) plus doxycycline (100 mg orally twice daily for 7 days)

7. Baseline and follow-up testing:

Proof of concept phase: (enrolled 50 participants in each group)

- (1) Questionnaire for socio-epidemiologic characteristics and sexual history at baseline and weeks 24, 48
- (2) Serum RPR at baseline and weeks 4, 12, 24, 36, and 48
- (3) *T. pallidum* PCR (TP-PCR) for self-collected specimens from oral rinse, urethral, and rectal sites at baseline, weeks 1, 2, 3, 4, 12, 24, 36, and 48 (specimens collected in weeks 1, 2, and 3 were optional)
- (4) Bacterial STIs (*C. trachomatis*, *N. gonorrhoeae*, *Mycoplasma genitalium*, *M. hominis*, *Ureaplasma urealyticum*, *U. parvum*) for self-collected specimens from oral rinse, urethral, and rectal sites at baseline and week 4
- (5) Resistance-associated mutations (RAM) of *T. pallidum* and other sexually transmitted bacteria at baseline

	Baseline	Wk1 (±2 days)	Wk2 (±2 days)	Wk3 (±2 days)	Wk4 (±2 days)	Wk12 (±2 weeks)	Wk24 (±2 weeks)	Wk36 (±2 weeks)	Wk48 (±2 weeks)
Questionnaire	v						v		v
Doxycycline compliance record		v							
RPR	v				v	v	v	v	v
TP-PCR	v	v	v	v	v	v	v	v	v
		(optional)							
Bacterial STIs	v				v				
RAM	v								

Continuation phase: (enrolled 100 participants in each group)

- (1) Questionnaire for socio-epidemiologic characteristics and sexual history at baseline and

weeks 24, 48

(2) Serum RPR at baseline and weeks 4, 12, 24, 36, and 48

(3) *T. pallidum* PCR (TP-PCR) for self-collected specimens from oral rinse, urethral, and rectal sites at baseline, weeks 4, 12, 24, 36, and 48

(4) Bacterial STIs (*C. trachomatis*, *N. gonorrhoeae*, *M. genitalium*, *M. hominis*, *U. urealyticum*, *U. parvum*) for self-collected specimens from oral rinse, urethral, and rectal sites at baseline and week 4

(5) Resistance-associated mutations (RAM) of *T. pallidum* and other sexually transmitted bacteria at baseline

	Baseline	Wk1 (±2 days)	Wk2 (±2 days)	Wk3 (±2 days)	Wk4 (±2 days)	Wk12 (±2 weeks)	Wk24 (±2 weeks)	Wk36 (±2 weeks)	Wk48 (±2 weeks)
Questionnaire	v						v		v
Doxycycline compliance record		v							
RPR	v				v	v	v	v	v

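### The 80% power at 150 per group has no stated allowance for missing data, although the ITT snapshot does not count no-data participants as successes

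*Combined protocol and SAP*

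**What the plan says.** The Statistical analysis section bases the sample size on a previous trial with six-month serological response of "90.2% in ceftriaxone group and 78.0% in BPG group". From this it sets a minimum of 150, described as the number "required for each treatment group to detect a between-group difference, with a two-sided significance level of 5% and a power of 80"%. It mentions no dropout or missing-data allowance.

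Methods 7 sets enrolment at 50 per group in the proof-of-concept phase ("enrolled 50 participants in each group") and 100 per group in the continuation phase. The total is 150 per group, with no surplus over the calculated number.

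The same statistical paragraph defines the ITT population as everyone randomised, apart from those who refuse use of their data. It applies the FDA snapshot, "which categorizes outcomes into success, failure, and no data in window". Categorical variables are compared by Fisher's "exact test or Chi-square test".

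Methods 11(2) adds that participants given a further antimicrobial active against *T. pallidum* "will also be excluded from the study".

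**The concern.** The power sentence and the analysis sit in one paragraph but do not describe the same comparison. The sample size treats 90.2% and 78.0% as the proportions to be compared among all 150 per group. In a snapshot, the success proportion has every ITT participant in the denominator. Each participant without a month-6 RPR therefore lowers the proportion. Equal missingness in both arms shrinks the difference and, at these rates, moves both proportions towards the middle of the scale, where the variance is larger. Both effects cost power.

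This is the only power figure in the plan. If it belongs only to nearly complete data, a reader who meets a non-significant difference will credit the trial with more ability to detect that difference than it had.

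**Working it through.** **Inputs.** p1 = 0.902, p2 = 0.780, n = 150 per group and two-sided α = 0.05 come from Statistical analysis. The 1:1 allocation is in Methods 6 and the 50 + 100 enrolment in Methods 7. The no-data rate m is not in the documents, so it is varied from 0 to 20%.

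**Reproducing the plan's figure.** With p̄ = (p1 + p2)/2 = 0.841, the uncorrected formula is

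n = [1.96·√(2p̄(1−p̄)) + 0.8416·√(p1(1−p1) + p2(1−p2))]² / (p1−p2)²

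= [1.96·√0.26744 + 0.8416·√0.26000]² / 0.122² = 2.081 / 0.014884 ≈ 140 per group.

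The continuity-corrected version gives 156. Exact enumeration of Fisher's test needs 153 for 80% and gives 0.7925 at 150. The stated pair (150, 80%) is thus reproduced to rounding by Fisher's test and is slightly conservative for the uncorrected chi-square. The plan does not say which method was used. All of these calculations assume no missing data.

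**Power under the snapshot.** If a fraction m in each arm has no data and counts as non-success, the proportions compared are p1(1−m) and p2(1−m), still with n = 150. The normal approximation is

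power = Φ{ [d − 1.96·√(2p̄(1−p̄)/n)] / √([p1(1−p1) + p2(1−p2)]/n) }, where d is the difference and the proportions are the reduced ones.

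- m = 0: (0.122 − 1.96 × 0.04222) / 0.04163 = 0.943, power 0.827.
- m = 0.10: proportions 0.8118 and 0.7020, d = 0.1098; (0.1098 − 1.96 × 0.04953) / 0.04912 = 0.259, power 0.602.

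The exact columns sum the two-binomial probabilities over all outcome pairs that the test rejects at 0.05.

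| No data, each arm (assumed) | Rates compared | Difference (points) | Chi-square, formula | Chi-square, exact | Fisher, exact |
|---|---|---|---|---|---|
| 0% | 90.2% v 78.0% | 12.2 | 0.8270 | 0.8343 | 0.7925 |
| 5% | 85.7% v 74.1% | 11.6 | 0.7089 | 0.7148 | 0.6630 |
| 10% | 81.2% v 70.2% | 11.0 | 0.6022 | 0.6060 | 0.5561 |
| 15% | 76.7% v 66.3% | 10.4 | 0.5117 | 0.5142 | 0.4655 |
| 20% | 72.2% v 62.4% | 9.8 | 0.4367 | 0.4368 | 0.3910 |

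Exact chi-square power is 0.801 at m = 1.4% and 0.796 at m = 1.6%. It therefore passes below 80% at about 1.5%, roughly two participants per arm (0.015 × 150 = 2.25). The formula puts the crossing at 1.2%.

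**Dropping no-data participants instead.** At 10% loss, n = 135 per group and the rates stay at 90.2% and 78.0%. Chi-square power is 0.786 by formula and 0.795 exactly. Most of the fall to 61% thus comes from counting no-data as non-success; the loss of numbers alone costs about 4 points.

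**The case against.** Several points on the other side have force.

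- **The source of the rates.** The documents do not say whether 90.2% and 78.0% are among assessed participants. If the cited trial already counted missing as failure, multiplying by (1−m) counts the loss twice and the true fall is smaller. This stands as a condition on every snapshot figure above.
- **A possible hidden allowance.** The uncorrected formula needs 140, so 150 could contain an allowance of 10/150, or about 7%. If no-data participants were dropped, power would stay near 80% up to about that loss. The plan does not claim such an allowance, and it would not protect a snapshot analysis.
- **The reading of the snapshot.** The plan does not spell out that no-data counts as non-success. That follows if response is successes over all ITT participants, which is the ordinary reading.
- **The design label.** Methods 1 calls the trial non-inferiority, whereas this power is for a difference. A reader might infer that the trial has only 50–60% power for its main question. The documents do not support that. As an illustration, borrow the 10% margin, which Methods 11 ties to the proof-of-concept phase. With 10% no data and the assumed rates, non-inferiority power is Φ[(0.10 + 0.1098)/0.04912 − 1.96] ≈ 99%. With both arms at 78.0% and complete data it is Φ[0.10/0.04783 − 1.96] ≈ 55%. The figures in the table answer neither question.
- **The antimicrobial exclusion.** A reader might infer that this rule also shrinks the response rates. It does so only if those participants stay in the denominator as non-successes. If they leave it, n falls and the rates do not shrink. Methods 11(2) and the ITT definition leave this open.
- **Fisher's test.** A reader might say that power is already short with complete data because Fisher gives 79%. Against a stated 80% that is rounding.

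**Conclusion.** The point holds as a mismatch between the power statement and the analysis. The stated 150 and 80% are not miscalculated. They carry no stated missing-data allowance, enrolment has no surplus, and the snapshot reaches 80% by chi-square only with almost complete data (no-data below about 1.5%).

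Over an assumed range of 5% to 20% no data, power to detect the difference falls from 71% to 44%. This rests on three assumptions: no-data equal in both arms, no-data counted as non-success, and cited rates that apply to assessed participants. No single value, including the 61% at 10%, should be read as the trial's actual power, because the plan gives no rate. It would also be too strong to say that the cited rates presuppose complete follow-up, since the documents are silent on that.

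**What to change.** Keep 150 per group and change the statistical text:

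1. Replace the 80% power claim with the power under the ITT snapshot at stated no-data rates, for one named chi-square-type primary comparison. For the uncorrected chi-square test, on the assumptions above, the figures are 71%, 61% and 51% at 5%, 10% and 15%. If Fisher's test is chosen instead, they are about 5 points lower.
2. State that no-data counts as non-success in the primary proportion, if that is intended, and whether the cited rates already count missing as failure. If they do, recompute.
3. State that this power is for detecting a difference and is not the power of a non-inferiority test.
4. Reconcile Methods 11(2) with the ITT definition, so that it is clear how participants removed for other active antimicrobials count in the primary analysis.

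The cost is wording and a less favourable stated power. No extra patients are needed. For scale only, restoring 80% at 10% no data would take 239 per group by the uncorrected formula; that increase is not requested here.

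### The declared non-inferiority trial rests on the ITT snapshot alone, with no observed-data or per-protocol analysis to show whether missing visits drive the month-6 result

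*Combined protocol and SAP*

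**What the plan says.** Methods item 1 calls the trial a "randomized controlled, open-label, non-inferiority study". Under item 6, "participants will be randomized in a 1:1 ratio". The primary outcome (item 9) is "Serologic response at month 6", which corresponds to the week-24 visit with its window of two weeks either side.

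The Statistical analysis section defines one population: everyone randomised, apart from those who refuse use of their data. It names one approach: "The analyses will be performed through the FDA snapshot algorithm in the ITT population". The snapshot sorts participants into three categories, the third for those without data in the visit window. The plan does not say how that category enters the between-arm comparison and gives no expected dropout. It contains no per-protocol, evaluable or observed-case set and no missing-data sensitivity analysis.

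The only margin is in Methods item 11(1), for the week-4 decision: "The non-inferiority margin of 10% will be used as the futility stopping rule in the proof-of-concept phase". For month 6 there is no margin and no confidence-interval rule. Item 11(2) removes from the study participants who receive other antimicrobials active against *T. pallidum*. The ITT definition does not say what becomes of them. Doxycycline intake is recorded as "the noting of tablet intake in the diary for the 7 days of the treatment period" (item 10(5)).

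**The concern.** Counting missing outcomes as non-successes is usually conservative in a superiority test, because it shrinks the observed difference. In a non-inferiority test the same shrinkage can favour the claim. If both arms lose similar fractions of participants, a ceftriaxone regimen that is truly worse by the full margin looks closer to BPG than it is.

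With one analysis set, a reader cannot tell whether a non-inferiority finding reflects efficacy or the pattern of missed visits. An analysis of those with a week-24 RPR, set beside the snapshot, would make that visible.

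**Working it through.** **Inputs from the plan.** 1:1 allocation; "at least 150 participants would be" needed per group; cited response rates "observed in 90.2% in ceftriaxone group and 78.0% in BPG group"; two-sided 5% level, 80% power.

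**Assumptions, because the plan is silent.**
- A 10-point margin at month 6, borrowed from the week-4 rule.
- Non-inferiority is claimed if the Wald lower 95% limit for ceftriaxone minus BPG lies above −10 points.
- No-data participants count as non-successes.
- Missing fractions of 0 to 20%, with loss unrelated to response within each arm.
- Truth at the margin: BPG 78% (the cited rate), ceftriaxone 78 − 10 = 68%.

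**Step 1: the plan's own figure.** For 90.2% v 78.0%, mean 0.841, the usual formula is

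n = [1.96·√(2·0.841·0.159) + 0.842·√(0.902·0.098 + 0.78·0.22)]² / 0.122² ≈ 140 per arm,

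or 156 with continuity correction. Fisher's exact test, which the plan names, has 79.3% power at 150 and 80.5% at 154. So 150 is about right for detecting a difference, and it is used below.

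**Step 2: equal loss.** With fraction m missing in each arm, observed success is 0.68(1−m) v 0.78(1−m), so the expected difference is −10(1−m) points. The false-claim rate comes from enumerating both binomials with n = 150 and adding the probability of every outcome that meets the claim rule.

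| m, both arms | Ceftriaxone | BPG | Expected difference | False claim |
|---|---|---|---|---|
| 0% | 68.0% | 78.0% | −10.0 | 2.5% |
| 5% | 64.6% | 74.1% | −9.5 | 3.1% |
| 10% | 61.2% | 70.2% | −9.0 | 3.8% |
| 15% | 57.8% | 66.3% | −8.5 | 4.5% |
| 20% | 54.4% | 62.4% | −8.0 | 5.7% |

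Check by normal approximation at m = 10%: SE = √(0.612·0.388/150 + 0.702·0.298/150) = 0.0546. The shift is 0.010/0.0546 = 0.18, and P(Z > 1.96 − 0.18) ≈ 3.8%.

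The base rate matters little. With truth 80% v 90% the rates are 2.7%, 4.1% and 5.7% at 0, 10 and 20% missing.

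**Step 3: observed data only.** At 15% missing, 127 per arm remain (150 × 0.85 = 127.5) and the rate is 2.5%. This relies on the assumption that loss is unrelated to response.

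**Step 4: unequal loss.** The expected difference is 0.68(1−m_C) − 0.78(1−m_B), where m_C and m_B are the missing fractions on ceftriaxone and BPG.
- 10% ceftriaxone, 15% BPG: 0.612 − 0.663 = −5.1 points; false claim 14.0%.
- 15% ceftriaxone, 10% BPG: 0.578 − 0.702 = −12.4 points; false claim 0.8%.

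The difference returns to −10 points when 0.68·m_C = 0.78·m_B, that is m_C = 1.15·m_B. At 10% missing on BPG this is 11.5% on ceftriaxone, about two more participants in 150.

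**The case against.** Four counter-arguments carry weight.

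- **Direction.** A reader might infer that missing data in the snapshot always favour non-inferiority. Step 4 shows otherwise: modestly greater loss on ceftriaxone cancels the effect, and more than that reverses it. The inflation holds for roughly balanced loss or for more loss on BPG.
- **The rule is borrowed.** The plan has no month-6 margin or interval rule. Its final comparisons are two-tailed tests at P<0.05, and its sample size targets a difference. Nor does it say that no data means non-success. The percentages therefore describe a rule that a non-inferiority claim would plausibly use, not one that the plan states.
- **Non-adherence.** A reader might add that missed tablets also pull the arms together. The documents do not support this. The injections are single doses, and doxycycline is common to both arms and described in the Background as an alternative syphilis treatment. A shared active drug may mask a difference between injections, so missed tablets could expose one. For the same reason, a per-protocol set restricted to full doxycycline takers is not necessarily the stricter check.
- **Data availability.** It is tempting to say that everything needed is already collected. The visit schedules list no record of other antimicrobials. Item 11(2) implies that such use is identified but names no data item.

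Per-protocol sets also carry selection bias, and the false-claim rate of the one proposed below was not computed. That is a reason to place it beside the ITT result rather than in its stead. None of these arguments supplies the missing supportive analysis.

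**Conclusion.** The gap is real: a declared non-inferiority trial has one analysis set and nothing to check it against. Its effect is modest under balanced loss at low rates and potentially large under unequal loss. The shrinkage by (1−m) under equal loss holds for any margin. The error rates hold only for the assumed 10-point month-6 margin, the non-success reading and the missing fractions tried.

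The documents do not support the stronger conclusion that the snapshot will produce a false claim. They support the narrower one that, in an open-label trial, the month-6 conclusion can turn on which arm misses visits and the plan as written would not reveal it.

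**What to change.** Keep the ITT snapshot and state that the no-data category counts as non-success. Beside it, report the month-6 risk difference with 95% CI in:

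1. participants with a week-24 RPR in window; and
2. a per-protocol set: assigned injection received, no other antimicrobial active against *T. pallidum* before the week-24 RPR, and that RPR available.

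Identify other antimicrobial use through the exclusion rule in Methods item 11(2), and reconcile that rule with the ITT definition. Treat completion of the doxycycline diary as a separate sensitivity cut, not a condition of the per-protocol set. Report no-data counts by arm.

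Pre-state one month-6 margin with its interval rule and judge every analysis against it. Draw an unqualified non-inferiority conclusion only if the snapshot and the supportive analyses agree.

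The cost is a short addition to the SAP, two further analyses and the diary sensitivity cut, mostly on data already scheduled. A record of other antimicrobial use may need to be made explicit. The downside is that a discordant result limits the claim.
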